The main outcome variables are to determine the effectiveness of remote wheelchair skills training include the Wheelchair Skills Test Questionnaire questions on capacity (WST-Q capacity) and confidence (WST-Q confidence), knowledge questions about wheelchair skills (WST knowledge), and remote evaluation through video analysis by the study team on capacity to perform skills. Additionally, we will gather feedback on how the training process could be improved.

2.18 Describe the statistical approaches that will be used to analyze the study data.

* Addressed below:

We will use a paired t-test to evaluate if there is an improvement in knowledge of skills following the respective training programs through knowledge based questionnaires for the trainees. We will determine if capacity and confidence increases through paired comparisons between baseline and follow-up for the WST-Q total scores. Capacity will also be evaluated based on whether participants are successful in each task as determined by a remote rater; in this success will be determined with at least 75% of participants achieving capacity in each task.

A power analysis was completed based on the published study completed with Occupational Therapy students with a pre-WSTP score of $64.8+/-9.0$ and post-WSTP score of $81.0+/-5.2$. Taking this into consideration, we will need a sample size of 23 individuals for a 95% power to detect a difference in the pre-WSTP and post-WSTP scores. We have estimated a sample size of 24 trainers and 72 trainees to account for participants who do not complete the study.

!Section: Section 5 - Potential Risks and Benefit

[reviewer notes.]

5.2

What steps will be taken in the event that a clinically significant, unexpected disease or condition is identified during the conduct of the study?

Not Applicable

[reviewer notes.]

5.8

Will any individuals other than the investigators/research staff involved in the conduct of this research study and authorized representatives of the University Research Conduct and Compliance Office (RCCO) be permitted access to research data/documents (including medical record information) associated with the conduct of this research study?

Yes

5.8.1

Identify the 'external' persons or entity who may have access to research data/documents and the purpose of this access:

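### Section 2.18: 23 individuals for 95% power does not follow from the cited pre/post scores; read as mean ± SD, they need at most 13 at two-sided 0.05

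*Combined protocol and SAP*

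**What the plan says.** Section 2.18 holds the only sample-size justification in the document. It takes its inputs from a published study in occupational therapy students, with a "pre-WSTP score of $64.8+/-9.0$ and post-WSTP score of $81.0+/-5.2", and states on that basis that "we will need a sample size of 23 individuals for a 95% power to detect a difference in the pre-WSTP and post-WSTP scores". Losses are handled in a separate, later step: "We have estimated a sample size of 24 trainers and 72 trainees to account for participants who do not complete the study".

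The planned tests are within-person. For knowledge, "We will use a paired t-test to evaluate if there is an improvement in knowledge of skills following the respective training programs"; for the questionnaire scores, "We will determine if capacity and confidence increases through paired comparisons between baseline and follow-up for the WST-Q total scores".

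The section does not say what ± denotes. It gives no alpha, sidedness, pre-post correlation or SD of change, names no target difference in points, and does not say whether the 23 individuals are trainers or trainees.

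**The concern.** The cited gain is 81.0 - 64.8 = 16.2 points, which is large against spreads of 9.0 and 5.2. A paired test of so large a change should need far fewer than 23 people for 95% power. The missing correlation does not obviously explain the gap, because two SDs put a ceiling on the SD of their difference.

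If the stated N and power do not belong to the cited effect, the reader cannot tell what change the study was designed to detect: the 16.2 points quoted, or something much smaller that is never named.

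**Working it through.** **Inputs from Section 2.18:** pre 64.8 ± 9.0; post 81.0 ± 5.2; power 95%; stated N 23; paired analysis.

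**Assumptions not in the plan:** ± is an SD; the target is 16.2 points; alpha is two-sided 0.05 unless noted. The correlation r is varied over its possible range.

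**Step 1. SD of change.** SD = √(9.0² + 5.2² - 2·r·9.0·5.2) = √(108.04 - 93.6·r). The largest possible value, at r = -1, is 9.0 + 5.2 = 14.20. The standardized change is 16.2/SD, so it is at least 16.2/14.20 = 1.14.

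**Step 2. Attempt to reproduce 23.** Smallest n with 95% power for a paired t-test (noncentral t, n - 1 degrees of freedom, noncentrality (16.2/SD)·√n):

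| r | SD of change | n, two-sided 0.05 | n, one-sided 0.05 | n, two-sided 0.01 |
|---|---|---|---|---|
| -1 | 14.20 | 13 | 10 | 18 |
| -0.5 | 12.44 | 10 | 8 | 14 |
| 0 | 10.39 | 8 | 7 | 11 |
| 0.5 | 7.83 | 6 | 5 | 8 |
| 0.9 | 4.88 | 4 | 3 | 6 |

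At r = -1 and two-sided 0.05, power is 0.948 with 12 pairs and 0.965 with 13. The value 23 does not appear. It is 23/13 = 1.8 times the worst-case requirement and 23/4 = 5.8 times the requirement at r = 0.9.

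**Step 3. Other routes to 23 with the same inputs.**
- Bonferroni correction of 0.05 for 2, 3 or 4 outcomes: at most 15, 16 or 17.
- Treating pre and post as independent groups, pooled SD √(108.04/2) = 7.35: 7 per group, 14 in total.
- Power of 99.9% in place of 95%, two-sided 0.05: at most 22.
- Stricter alpha: at r = -1, 23 is the smallest n only for two-sided alpha of about 0.0015 to 0.0020.
- Dropout: the plan applies it after the 23, so it is not the source.

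**Step 4. Power that 23 pairs actually give for 16.2 points.** At two-sided 0.05: 0.9994 at r = -1, 0.99997 at r = -0.5 and above 0.999999 at r = 0. At two-sided 0.01, r = -1: 0.993.

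**Step 5. What would make 23 right.** At two-sided 0.05 and 95% power, 23 is the smallest n for a standardized change of about 0.79 to just under 0.81. For 16.2 points that means an SD of change of 20.1 to 20.6, against a maximum of 14.20 (20.1/14.20 = 1.4). Turned round, 23 pairs detect 0.787 × SD of change: 11.2 points at r = -1, 9.8 at -0.5, 8.2 at 0, 6.2 at 0.5 and 3.8 at 0.9.

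**Step 6. Other meanings of ±** (two-sided 0.05, 95% power, 16.2 points; m is the published sample size, which the plan does not give). If ± is a 95% confidence-interval half-width, n = 23 results at m = 17 (r = 0) or m = 28 to 29 (r = 0.5). If it is a standard error, n = 23 results at m = 8 (r = 0.6), 11 (r = 0.75) or 17 (r = 0.9).

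**The case against.** The strongest reply is that the mismatch is conditional. The plan does not say that ± is an SD, and Step 6 shows that other readings reproduce 23 for several combinations of published sample size and correlation. Nor does the plan say that the target is 16.2 points: it says only that the published scores were taken into account. A standardized change of 0.8 gives exactly 23 at two-sided 0.05 and 95% power, and a more cautious target could be sensible where remotely trained clinicians go on to teach others. On that view the fault is an undisclosed input, not wrong arithmetic.

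This stands as a limit on the conclusion: the origin of 23 cannot be established from the document. It does not rescue the sentence. Mean ± SD is the usual reading, and the text presents 23 as following from those scores. Every alternative needs a figure that the plan omits.

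A second reply is that enrolment should not be called safe on this calculation alone. The outcomes include questionnaire capacity, confidence and knowledge, not only the cited score, and Section 6.2.2 lets one trainer teach up to 3 trainees, so trainees may be clustered. That is fair. The reassurance is limited to the 16.2-point gain at conventional alpha with independent pairs. Even if each trainer's trainees counted as a single unit, the 24 planned trainers would exceed the worst-case 13.

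**Conclusion.** The point holds, as a minor one. If ± is an SD, the target is the cited 16.2 points and alpha is conventional, the stated 23 and 95% cannot both be right at any pre-post correlation. The bound of 13 does not depend on guessing the correlation. Confidence is moderate, because the meaning of ± and the target are inferred. The discrepancy errs on the safe side: the study is not underpowered for the effect it cites. What is lost is a reader's ability to say what effect the sample size was chosen for.

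**What to change.** Rewrite the power paragraph in Section 2.18. Label the ±, and state alpha, sidedness, the SD of change (or the pre-post correlation), the target difference, and whether the individuals are trainers or trainees. Then, according to what was actually planned:

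1. If 16.2 points is the target and ± is an SD, report the N it needs: about 8 at r = 0 and at most 13 at any correlation (two-sided 0.05, 95% power).
2. If a smaller target was intended, keep 23 and say that it gives 95% power at two-sided 0.05 for a standardized mean change of about 0.79 in independent individuals, with the equivalent in points for the assumed correlation. The target should be the one used in planning, not one worked back from 23.
3. If ± is not an SD, say so and give the published sample size so that 23 can be reproduced.

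The cost is one paragraph. The planned 24 trainers and 72 trainees and the analysis need not change for this reason.

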If Industry support, provide the sponsor information and level of support:

If Foundation support, provide the sponsor information:

If Other support, provide the support information and level of support:

[reviewer notes.]

7.3

Is this study funded in part or whole by a PHS Agency?

No

Does any investigator* involved in this study (select all that apply):

Name

A. Have equity in a **publicly-traded entity that either sponsors** this research or owns the technology being evaluated or developed that exceeds a **5% ownership interest** or a current value of **\$10,000**?**

B. Have equity in a **non-publicly-traded entity that either sponsors this research or owns the technology being evaluated or developed?**

C. Receive salary, consulting fees, honoraria, royalties or other remuneration from an entity that either sponsors this research or owns the technology being evaluated or developed that is expected to exceed **\$10,000 during the past or next 12 months?**

D. Have rights as either the author or inventor of **intellectual property being evaluated or developed in this research that is the subject of an issued patent or has been optioned or licensed to an entity?**

E. Have an officer or management position** with a **Licensed Start-up Company** overseen by the CO! Committee that either sponsors this research or owns the technology. being evaluated or developed?**

F. Receive compensation of any amount when the value of the compensation would be affected by the outcome of this research, such as compensation that is explicitly greater for a favorable outcome than for an unfavorable outcome or compensation in the form of an equity interest in the entity that either sponsors this research or owns the technology being evaluated or developed?

None of the above options apply and there are no other financial conflicts of interest in the conduct of this research.

!section: Section 7 - Qualifications and Source(s) of Support

***Investigator** means the PI, co-investigators, and any other member of the study team, regardless of title, who participates in the design, conduct, or reporting of this research, as well as his/her spouse, registered domestic partner, dependents, or other members of his/her household. **The PI is responsible for ensuring that/s/he and all other relevant members of the study team review the above questions describing Significant Financial Interests.**

**through the provision of funds, drugs, devices, or other support for this research

****Such as serving on the Board of Directors or Board of Managers or a position that carries a fiduciary responsibility to the company (e.g., CEO, CFO, CTO, or CMO).

@ection: Supporting Documentation!

[reviewer notes-]

Supporting Documentation Section

References and Other Attachments

Additional documents:

Modified

Name Date

Version

Please use the Add button to the left to upload additional documents if needed.

[reviewer notes-]

ClinicalTrials.gov is a registry and results database of publicly and privately supported clinical studies of human participants conducted around the world.

"Applicable clinical trials" are required by **federal law** to be registered in **ClinicalTrials.gov**.

Applicable Clinical Trials (ACTs) are studies that meet the following criteria:

- The study is an interventional study AND
- The study intervention is a drug, biologic, medical device, radiation or genetic AND
- The Study is not Phase 0 or 1 AND
- The study has at least one site in the United States or is conducted under an investigational new drug application or investigational device exemption

NIH Policy

Effective January 18, 2017, revised **NIH** Policy requires that all **clinical trials** funded in whole or in part by the NIH be registered and results information posted on ClinicalTrials.gov.

As defined by the NIH, a **clinical trial** is:

A research study in which one or more human subjects are prospectively assigned to one or more interventions (which may include placebo or other control) to evaluate the effects of those interventions on health related biomedical or behavioral outcomes.

The NIH Policy extends beyond the Food and Drug Administration Amendment Act (FDAAA 801) requirements in that it requires registration and results reporting of:

- clinical trials of behavioral, surgical and other types of health and medical interventions
- phase 1 studies of drugs and biological products
- small feasibility studies of device products

Failure to submit all required registration and results information requested on ClinicalTrials.gov can jeopardize University grant funding, the future funding of the grantee and subject the University of Pittsburgh to future monetary penalties.

In addition, to promote transparency of the clinical trials process, the **International Committee of Medical Journal Editors (ICMJE)** has established a policy requiring the entry of clinical trials in a public registry, such as ClinicalTrials.gov, prior to subject enrollment as a condition of consideration for publication of the trial results.

ection: Supporting Documentation!

* Based on the above information, will this study be registered in ClinicalTrials.gov?
No
